#### 4.6. Study Outcome Measures and Ascertainment

##### 4.6.1. Primary Outcome

**Fetal C-peptide levels (in mg/dL), measured in umbilical venous blood**

##### 4.6.2. Neonatal Secondary Outcomes

1. Fetal cortisol, insulin-like growth factor, leptin, and other hormonal and metabolic markers
2. NICU admission and length of stay
3. Neonatal hypoglycemia, defined as CBG < 40mg/dL within the first 48 hours of life
4. Neonatal blood glucose nadir (in mg/dL)
5. Timing of neonatal blood glucose nadir (in minutes of life)
6. Severe neonatal hypoglycemia, defined as composite of:
  - a. CBG < 25mg/dL at 0-4 hours of life
  - b. CBG < 35mg/dL at 4-24 hours of life
7. Symptomatic hypoglycemia, defined as CBG < 40 and one of the following: poor feeding, irritability, tremors, jitteriness, exaggerated Moro reflex, lethargy, seizure, poor tone, persistent hypothermia
8. Neonatal hypoglycemia treatment (i.e. measurable feeding, glucose gel, glucose-containing IVF)
9. First repeat neonatal blood glucose after treatment
10. Seizures or encephalopathy due to hypoglycemia
11. Neonatal mortality

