### 4.4. Patient Management and Follow-up

Other than the timing and frequency of maternal glucose screening and recommended thresholds for treatment of hyperglycemia detailed in the study protocol, women will receive standard care as defined by their clinical provider. Women randomized to the intervention arm will undergo screening for and treatment of maternal hyperglycemia until delivery or hospital discharge for a maximum of 5 days following BMZ.

All study neonates will have CBG testing within 2 hours of life. This is standard of care for neonates born at less than 37 weeks. As part of the study protocol, CBG will be measured within 2 hours of life on those neonates who are delivered at or after 37 weeks and 0 days. The remainder of neonatal care will be according to the clinical provider. Umbilical cord blood and placental samples will be collected after delivery to evaluate fetal metabolic status in utero as well as other genetic changes. All study specimens will be labeled with a unique study ID code. Personnel responsible for lab assays will receive the specimens in a coded fashion without any documentation of PHI or study arm.

- Placental biopsies:
  - 15 punch biopsies will be obtained from each placenta using a standard 3mm punch biopsy tool. Biopsies should be obtained 2 cm from the cord insertion site.
  - Three punch biopsy samples will be placed into 5 separate aliquot tubes.
  - 0.5mL AllProtect solution will be placed in 3 of the 5 aliquot tubes
  - The other 2 aliquot tubes will be empty
- Placental portions:
  - 2 placental portions should be removed using sharp dissection (scalpel or scissors). Each portion should measure approximately 0.5 by 0.5 inches and should traverse the complete depth of the placenta.
  - Each placental portion should be placed into a 15mL falcon tube
  - The distance from the cord insertion should be recorded. One portion should be removed 2 cm from the cord insertion. The other should be removed 2 cm from the periphery.

While maternal CBG will only be performed for maximum of 5 days following BMZ, maternal postpartum data will be collected through hospital discharge. Neonatal data will be collected through hospital discharge or until 28 days of life.

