**Analysis Plan for Aim 2 (BMZ-exposed subjects in usual care group vs intervention group):**

Cord blood C-peptide levels will be compared between randomized arms (usual care vs. screening/treatment after BMZ) using a linear model, controlling for gestational age at randomization. We will estimate the mean difference between groups along with a 95% confidence interval. Similar models will be used to compare 2° metabolic measurements such as cord blood cortisol, insulin-like growth factor, and leptin levels between BMZ-exposed usual care vs. BMZ-exposed intervention group. Metabolic and hormonal analytes will be correlated with our exploratory outcomes: neonatal hypoglycemia (defined as neonatal glucose < 40mg/dL within 48 hours of birth), NICU admission, and NICU stay  $\geq$  72 hours.

If the 2 groups show a difference in the 1° outcome, interactions will be evaluated using linear regression models and subgroup analyses conducted to determine whether the effect differs across particular subgroups of patients. In particular we will assess subgroups defined by gestational age (dichotomized at 36 wks), interval from BMZ exposure to delivery (dichotomized at 3 days), maternal obesity (defined as BMI  $\geq$  30 kg/m^2 at time of delivery), race/ethnicity, and expected indication for late preterm delivery at trial entry (preterm premature rupture of membranes vs. preterm labor vs. obstetrical/medical indication). We will conduct 2° analyses to examine neonatal sex (male vs. female) on the 1° outcome.

We will use linear regression models to assess the association between randomization arm, time since first dose of BMZ until delivery, doses of BMZ received, and the interactions of the latter two with each of the study arm approaches (usual care vs. screening/treatment). We will estimate the association between time interval to delivery and number of BMZ doses separately in each study arm and compare the associations between arms.

Loss to follow-up will be defined as the inability to ascertain whether the neonate was born alive and if born alive umbilical cord blood not collected. Those defined as lost to follow-up will not be included in the primary analysis. It is expected that the loss to follow-up rate will be very low, less than 10 percent. However, a sensitivity analysis will be performed including patients lost to follow-up with “worst case” assumptions regarding their outcome to determine whether the results are robust.

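### Neonatal hypoglycemia, severe hypoglycemia and glucose nadir depend on how often each baby is tested, yet only one test is scheduled for every baby and that value is not an outcome

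*Combined protocol and SAP*

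**What the plan says.** Section 4.4 (Patient Management and Follow-up) fixes one neonatal glucose measurement: "All study neonates will have CBG testing within 2 hours of life". For births before 37 weeks this is described as standard care; for births at or after 37 weeks 0 days it is done because the protocol requires it. The section continues: "The remainder of neonatal care will be according to the clinical provider". No later neonatal test is scheduled anywhere in the documents. The Neonatal Glucose Log, under Data Collection Forms, records the measurements that are made and sets no times for them.

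Section 4.6.2 lists these glucose outcomes:

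- Item 3: "Neonatal hypoglycemia, defined as CBG < 40mg/dL within the first 48 hours of life".
- Items 4 and 5: the glucose nadir and the time at which it occurs, with no window for either.
- Item 6: severe hypoglycemia, a composite of one threshold at 0-4 hours and a second, "CBG < 35mg/dL at 4-24 hours of life".
- Item 9: "First repeat neonatal blood glucose after treatment", which exists only for treated babies.

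The first CBG, which every baby has, is not on the list. The Analysis Plan for Aim 2 uses the same 48-hour definition of hypoglycemia, calls it exploratory, and correlates the cord analytes with it. Section 3.2 asks whether screening and treatment lower the prevalence of neonatal hypoglycemia.

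**The concern.** Items 3 and 6 are met if any reading in a window is low, and items 4 and 5 describe the lowest reading and when it fell. All of them can change when another test is added: the chance of at least one low value can only rise, and the nadir can only fall. With a common schedule this would matter little. Here only one test is common to all babies, and none is scheduled in the 4-24 hour window of item 6. A baby with only the study test has a nadir equal to that value and a nadir time of at most 2 hours.

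Randomization does not settle this, because the amount of testing arises after allocation. One arm has maternal glucose checks and insulin, the other has neither, and there is no sham. The only masking described is for the laboratory staff. A neonatal team that knows the mother received insulin might watch her baby more closely; a team reassured by good maternal control might do the opposite. More testing in the intervention arm could hide or reverse a benefit, and less testing could create one. Section 2.4 expects a reduction in neonatal hypoglycemia and presents the study as the foundation for a larger trial, so an error in either direction could carry forward.

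**Working it through.** The documents give no power or rate calculation for these outcomes, so there is no figure to reproduce. The check compares schedule with windows, then illustrates the size.

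**Schedule against windows**

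| Outcome (4.6.2) | Window | Study test scheduled in the window |
|---|---|---|
| Item 3, any CBG below 40 mg/dL | 0-48 h | One, within 2 h |
| Items 4 and 5, nadir and its time | None stated | One, within 2 h |
| Item 6, first part | 0-4 h | One, within 2 h |
| Item 6, second part | 4-24 h | None |

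**Illustration 1.** Assumptions, none taken from the documents: each reading has a 15% chance of being below 40 mg/dL, readings are normal with within-baby correlation ρ, the number of tests does not depend on earlier results, and the arms are truly equal. With c = Φ⁻¹(0.15) = -1.036 and baby effect u,

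P(any of k readings low) = 1 - ∫ φ(u) [1 - Φ((c - √ρ·u)/√(1-ρ))]^k du.

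| ρ | k = 1 | k = 3 | k = 4 | k = 6 | 4 v 3 | 6 v 3 |
|---|---|---|---|---|---|---|
| 0.3 | 15.0% | 34.1% | 40.7% | 50.5% | 6.6 points | 16.4 points |
| 0.5 | 15.0% | 30.8% | 35.8% | 43.0% | 5.0 points | 12.2 points |
| 0.7 | 15.0% | 26.9% | 30.3% | 35.2% | 3.4 points | 8.3 points |

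At ρ = 0.5 the expected nadir is -0.60 SD with three tests and -0.90 SD with six, a shift of 0.30 SD.

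**Illustration 2, anchored to a per-baby rate.** Section 2.2 reports 24% hypoglycemia with betamethasone and 15% with placebo. Assume SD 15 mg/dL and set the mean so that four readings give 24% below 40 mg/dL. Over correlations from 0 to 0.6, by simulation:

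- three tests: 18.7% (correlation 0) to 20.6% (0.6)
- four tests: 24.0% by construction
- six tests: 33.8% (correlation 0) to 29.2% (0.6)

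So 4 v 3 gives 24.0 - 20.6 = 3.4 to 24.0 - 18.7 = 5.3 points, and the mean nadir shifts by 1.7 to 2.8 mg/dL. For 6 v 3 the gap is 29.2 - 20.6 = 8.6 to 33.8 - 18.7 = 15.1 points.

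**Against the trial's size.** After 10% loss there are 144 × 0.9 / 2 ≈ 65 babies per arm. With no true effect, a two-sided 5% test would find more hypoglycemia in the more-tested arm with probability 7-11% for 4 v 3 tests and 20-50% for 6 v 3 (Illustration 2), where 2.5% is nominal. For comparison, power to detect 24% v 15% with 65 per arm is about 25%; 80% power needs 304 per arm.

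**The case against.** Several points on the other side carry weight.

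- **Testing may be largely routine.** Section 2.4 quotes a society statement supporting routine postnatal testing of late preterm newborns, so later tests probably happen, and in much the same way in both arms. Stratification by site (section 3.6) balances differences between hospitals. Only a within-site difference by arm would bias the comparison. This stands and limits the likely size, but the statement sets no study schedule and does not cover babies born at or after 37 weeks. Those babies should be a minority, since planned delivery at that age is an exclusion.
- **Repeats after a low value cannot change item 3.** Such a baby is already classified, so raw test counts overstate the effect if the extra tests are mostly follow-up of low readings. This stands for item 3. The nadir and its time can still move.
- **15% per reading is high.** In section 2.2, 15% is a rate per neonate, in the placebo group. Anchoring to 24% per neonate leaves the gaps similar.
- **A detailed SAP was promised before the first enrolment** and may set derivation rules. The plan supplied does not contain them.

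A reader might also infer more than the documents support. They do not state that neonatal teams know the arm or test differently by arm, and nothing supports six tests against three; that case only shows how the error grows. Nor do they show bias in the planned correlations with cord analytes: samples are assayed under codes, and nothing says that results reach the neonatal team. Finally, they do not show that the first CBG should replace the 48-hour outcome. Section 3.2 asks about prevalence, degree and duration, which one early reading cannot answer, and a test within 2 hours may fall at any minute from 0 to 120.

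**Conclusion.** The point holds for the secondary outcomes in items 3 to 6. As written, the plan could show a between-arm difference, or conceal one, through testing frequency alone, and it offers no comparison free of that dependence. Only item 3 has a 48-hour window. Item 6 ends at 24 hours, and the nadir items have none, which leaves them more exposed.

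A fair size is the effect of one extra test in one arm: about 5 percentage points at correlation 0.5, and 3 to 7 across both illustrations. That is roughly half of the 9-point difference (24% - 15%) that motivates the trial. Test counts, correlations and SD are assumptions. That the outcomes depend on test count follows from their definitions; that testing would differ by arm is an inference.

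The consequence is bounded. The primary outcome does not depend on neonatal testing, hypoglycemia is called exploratory in Aim 2, and power for it is low in any case. The matter is still worth settling, because the remedy uses data already collected and is credible only if chosen before outcomes are seen by arm.

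**What to change.** - In section 4.6.2, add the first neonatal CBG within 2 hours of life, as a value in mg/dL and as below 40 mg/dL, as a secondary outcome compared between arms alongside the 48-hour outcome.
- State one common window for the nadir and its timing (items 4 and 5).
- Report by arm the number of CBGs and the hours of testing per neonate, and interpret items 3 to 6 in that light.
- Keep the 48-hour outcome and the Aim 2 correlations as planned.

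The cost is a change of wording and a few variables derived from the existing Neonatal Glucose Log, with no extra blood test and no change to neonatal care. The drawbacks are one more secondary comparison and that the first CBG misses later episodes, which is why the 48-hour outcome stays.

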##### 4.6.3. Maternal Secondary Outcomes

1. Maternal hyperglycemia, defined as intrapartum CBG >100 mg/dL, fasting CBG >95mg/dL or 1-hour postprandial CBG >140mg/dL
2. Maternal treatment with insulin (total units required)
3. Maternal hypoglycemia, defined as CBG < 60 mg/dL or < 80 mg/dL with symptoms including hunger or nausea, lightheadedness or dizziness, sweating or chills, irritability, tingling or numbness in lips or tongue, weakness or fatigue, seizure, loss of consciousness

#### 5. Statistical Considerations

##### 5.1. Sample Size and Power

For the ALPS trial at UNC-CH we annually enrolled 40-50% of all late PTBs. Thus, during the 18 month recruitment for this proposed study, we expect ~300 women to present with threatened late PTB and 144 who will enroll and be randomized (72/group). We expect no more than 10% loss to follow-up with a total of 70% delivering within 3 days of BMZ (50/group) during the period of maternal hyperglycemia when our intervention has the greatest benefit.

**Table 4. Power for Sample Size = 144 ( $\alpha=0.05$ )**

---

As shown in Table 4, this sample size provides reasonable power to detect a clinically meaningful difference in C-peptide levels between the intervention and usual care groups after BMZ exposure. This calculation was performed using a range of expected

Power (%) if 10% loss to follow-up (n=130)	Power (%) for subgroup if 70% deliver in 3 days (n=100)	Mean difference in C-peptide level (mcg/L)	Standard deviation	Sample size needed
95	85	0.5	0.75	84 (42/group)
95	90	1	1.5	98 (49/group)
90	80	1.5	2.5	90 (45/group)
98	90	1.5	2	78 (39/group)

primary outcomes based on previously reported values (normal C-peptide 0.6-1.0mcg/L, 95th percentile C-peptide 1.77mcg/L, C-peptide after antenatal BMZ exposure 2.85mcg/L) under conservative scenarios. Further, this sample size will be sufficient to detect differences in cortisol and insulin-like growth factor between these groups with more than 80-90% power based on previously reported values and the same assumptions above.

In addition to these 144 women enrolled prospectively, we will have access to 75 umbilical cord blood samples from the MOTOR trial. With this available sample size based on the same conservative scenarios in Table 4, we will have ≥80% power to compare C-peptide levels between unexposed controls and women exposed to BMZ who are randomized to usual care.

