## 5.2. Interim Analysis

The Data and Safety Monitoring Board meets monthly; however, a formal interim analyses for overwhelming efficacy is planned after 50% of recruitment is completed (n=75). For the planned interim analysis, a formal detailed statistical report will be written by [name], Biostatistician including protocol adherence, the primary outcome, and adverse events reported as well as center performance in terms of recruitment, data quality, loss to follow-up and protocol violations.

The main statistical issue relevant to interim analysis is the problem of performing multiple tests of significance on accumulating data. A number of procedures have been developed to handle this situation. For this trial, the group sequential method will be used to control the type I error with the Lan-DeMets spending function and the O’Brien-Fleming type boundary. Assuming that the analysis is conducted at precisely 50%, this implies that the alphas to be used will be 0.003 and 0.049 at the interim and final analyses, respectively. However, this should not preclude the Data and Safety Monitoring Board recommending termination earlier if there is evidence of harm. Pre-specified stopping rules for safety will be developed.

It is recognized that any decision to terminate the study would not be reached solely on statistical grounds but on a number of complex clinical and statistical considerations.

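### Table 4's 3-day subgroup column is not the power at its labelled n=100: two rows with the same effect size show 85% and 90%, and all four figures match unstated target powers

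*Combined protocol and SAP*

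**What the plan says.** Section 5.1 expects "144 who will enroll and be randomized (72/group", and then "no more than 10% loss to follow-up with a total of 70% delivering within 3 days of BMZ (50/group". Table 4, at alpha 0.05, turns this into two power columns. The first is headed "Power (%) if 10% loss to follow-up (n=130" and the second "Power (%) for subgroup if 70% deliver in 3 days (n=100". A last column gives a required sample size but no target power.

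| Row | Difference / SD (mcg/L) | Power, n=130 | Power, n=100 | Required size |
|---|---|---|---|---|
| 1 | 0.5 / 0.75 | 95 | 85 | 84 (42/group) |
| 2 (bold) | 1 / 1.5 | 95 | 90 | 98 (49/group) |
| 3 | 1.5 / 2.5 | 90 | 80 | 90 (45/group) |
| 4 | 1.5 / 2 | 98 | 90 | 78 (39/group) |

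The Analysis Plan for Aim 2 lists "interval from BMZ exposure to delivery (dichotomized at 3 days" among its subgroups. Section 5.2 adds one interim look: "this implies that the alphas to be used will be 0.003 and 0.049 at the interim and final analyses, respectively".

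**The concern.** Power for a two-group comparison of means depends on the difference and the SD only through their ratio. Rows 1 and 2 have the same ratio, yet they carry different powers under one labelled n and different required sizes. No choice of n, alpha or sidedness allows that, so the column cannot be what its heading says.

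Table 4 is the only power justification for 144 women, and Section 5.1 singles out the 3-day window as the period when the intervention should help most. Section 5.1 also reuses the Table 4 scenarios for the Aim 1 comparison, and the same assumptions for cortisol and insulin-like growth factor. A reader who takes the table at face value gets the wrong power for the 3-day subgroup and cannot see what power each required size is meant to deliver.

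**Working it through.** **Inputs.** Differences, SDs, alpha 0.05 and the n labels come from Table 4; 144 women, 10% loss and 70% early delivery come from Section 5.1. Sidedness is not stated in Table 4. I take two-sided and test that choice in step 2.

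**Method.** Two-sample t-test with n per group, d = difference/SD, df = 2n − 2 and noncentrality d√(n/2). Power is the probability that the noncentral t exceeds the two-sided critical value in absolute size.

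**Step 1, effect sizes.** 0.5/0.75 = 0.667; 1/1.5 = 0.667; 1.5/2.5 = 0.600; 1.5/2 = 0.750.

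**Step 2, the plan's own required sizes.** Using the subgroup column as target power, the smallest n per group is:

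| Row | d | Target taken from column 2 | n/group, two-sided | n/group, one-sided | Table 4 |
|---|---|---|---|---|---|
| 1 | 0.667 | 85% | 42 | 34 | 42 |
| 2 | 0.667 | 90% | 49 | 40 | 49 |
| 3 | 0.600 | 80% | 45 | 36 | 45 |
| 4 | 0.750 | 90% | 39 | 32 | 39 |

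The two-sided t-test reproduces all four entries exactly. The normal approximation gives 41, 48, 44 and 38.

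**Step 3, the subgroup column at its label.** With n = 50 per group the noncentrality is d√25 = 5d, that is 3.33, 3.33, 3.00 and 3.75.

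| Row | Stated | Power at n=100 | Gap (points) |
|---|---|---|---|
| 1 | 85 | 91.0 | 6.0 |
| 2 | 90 | 91.0 | 1.0 |
| 3 | 80 | 84.4 | 4.4 |
| 4 | 90 | 96.0 | 6.0 |

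One-sided testing moves further away (95.2, 95.2, 90.9, 98.1). Between 30 and 72 per group, no n brings all four rows within 3.5 points of the stated figures.

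**Step 4, the first column at its label.** At 65 per group: 96.5, 96.5, 92.4 and 98.9%, against the stated 95, 95, 90 and 98. The gaps are 1.5, 1.5, 2.4 and 0.9 points. The printed figures fit 59–60 per group (118–120 women) better than 65: at 59 per group the powers are 94.9, 94.9, 89.8 and 98.1.

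**Step 5, is 50 per group net of loss?** 0.9 × 144 = 129.6, which is the 130. 0.7 × 144 = 100.8, which is the 100 with no loss removed. Applying both, 0.9 × 0.7 × 144 = 90.7. At 45 + 46 women the powers are 88.2, 88.2, 80.8 and 94.3%. Only the bold row then falls below its stated figure, by 90 − 88.2 = 1.8 points. That row needs 98 women, which 100.8 supplies as long as loss in the subgroup is at most 1 − 98/100.8 = 2.8%.

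**Step 6, final-look alpha of 0.049.** n=100: 90.9, 90.9, 84.2, 95.9. n=130: 96.4, 96.4, 92.3, 98.9. n=91: 88.0, 88.0, 80.6, 94.2. No figure moves by more than 0.3 points.

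**Step 7, required size at one common target.** At 90%: 49, 49, 60 and 39 per group, that is 98, 98, 120 and 78 women. Row 3's printed 90 women is an 80% figure.

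**The case against.** The best reply is that this is a reporting slip with no effect on the trial. At the labelled n both columns understate power in every row. The bold scenario is right to within 1 point, and most of the table is in round figures. The text claims only reasonable power under conservative assumptions, which is true. The Aim 1 claim of at least 80% also survives: 75 v 50 gives 95, 95, 90 and 98%, and 75 v 45 gives 94, 94, 88 and 98%. The Aim 2 subgroup analyses are run only if the primary outcome differs between arms.

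All of that stands, and it limits the weight of the point. So do three narrower objections:

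- That column 2 holds target powers is an inference; the plan does not say so. Four exact matches make it a strong one.
- The first-column gap is small. Rounding may explain part of it, and the fit at 118–120 women is not unique: 75 v 50 rounds to the same four figures.
- The planned 95% confidence intervals already point to two-sided testing.

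Rounding does not rescue the subgroup column. Rounded down to a multiple of 5, rows 1 and 4 would read 90 and 95, not 85 and 90. Nor does it explain two different required sizes for one effect size.

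**Conclusion.** The point holds. Column 2 of Table 4 is not the power at n=100: rows 1, 3 and 4 are understated by 6.0, 4.4 and 6.0 points, and row 2 by 1.0. The required sizes are correct only if each row has its own target (85, 90, 80 and 90%), which the table does not state. Column 1 is low by 0.9 to 2.4 points, a lesser matter.

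These figures assume a two-sided t-test at 0.05 with equal groups. The adequacy of 144 women for the primary intention-to-treat comparison is not in question. The one adverse case is the bold row at about 88% instead of 90%. It needs the full 10% loss to occur, to fall equally on early deliverers, and not to be already inside the 70%; the wording in Section 5.1 leaves that last point open.

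**What to change.** 1. Either restate column 2 as 91, 91, 84 and 96% at n=100, or relabel it as the target power behind each required size and add a true n=100 column.
2. Say in one sentence whether 50 per group is net of loss. If it is not, label the column n = about 91 (45–46 per group) and give 88, 88, 81 and 94%.
3. Restate column 1 as 97, 97, 92 and 99% at n=130.
4. State the target power for each required size. A single target is easier to read (at 90%: 98, 98, 120 and 78 women), but different targets are acceptable if labelled.
5. State that the test is two-sided.

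While the section is open, reconcile a separate discrepancy: Section 4.6.1 defines the primary outcome as "Fetal C-peptide levels (in mg/dL), measured in umbilical venous blood", whereas Table 4 and its supporting values are in mcg/L.

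The cost is a corrected table, one sentence on loss and one unit. The design and sample size do not change.
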